#### **D.5. Analysis of Secondary Hypothesis - Adherence**

**Do veterans randomized to the titrated disease management arm have greater medication adherence than veterans randomized to the control arm?**

As described in the measures section C.20.d, medication adherence will be calculated by applying the ReComp algorithm to local VA pharmacy records (i.e., medication name, date dispensed, the number of days supply dispensed). ReComp values can be any value greater than or equal to 0, with the range between 0 and 1 representing the proportion of days that a medication was available to the patient, and values over 1 representing oversupply of medication. Medication adherence will be calculated for each veteran at baseline and each month of follow up, so the unit of analysis is the person-month. We will operationalize adherence as both a continuous and dichotomous variable as described above under measures. Examining adherence as a continuous variable (as opposed to dichotomizing adherent vs. not adherent) will allow for assessment of over-supply and the association between over-supply and systolic blood pressure.

The impact of the intervention upon continuous medication adherence will be tested with a general linear model as described above for systolic blood pressure. Again, we will use the SAS procedure MIXED to estimate the model and test the difference in medication adherence at 18 months. We plan to model the probability of being adherent over time and test this secondary hypothesis using generalized linear mixed models as applied in PROC GLIMMIX with adaptive quadrature. The mixed model will include time, the treatment by time interaction (with time dummy coded), and the stratification variables. To account for the within-patient correlation over time, we have found that either a random intercept-slope (i.e., growth curve model) specification for the random effects or an unstructured covariance matrix is most appropriate.

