#### **C.3.b. Inclusion Criteria Determined During Initial Screening Phone Call with Potential Subjects.**

Patients must indicate that they both:

- Have a VA or affiliated clinic provider that they consider to be their main PCP.
- Receive the majority of healthcare at the Durham VAMC (or affiliated clinic).

These inclusion criteria are used to ensure that patients in the trial consider themselves to be VA primary care patients who are receiving hypertension care in the VA. We conceive of this pragmatic trial as informing interventions that would be suggested by the PACT/PCMH model. Key to this model is the integration of patient-responsive services within a care team. Clinicians in this study will have the ability to communicate with the patients care team. This link to primary care differentiates the proposed program and eventual implementation from stand-alone disease management programs that may be provided by outside groups. Our approach is supported, by the PACT/PCMH and the Chronic Care Model. In a 2006 mailed survey of Durham VAMC patients with diabetes that we conducted, 17% respondents reported that they do not have a PCP at the Durham VAMC who provides the majority of their diabetes care. If a patient switches to another VA facility during our study we will no longer conduct monthly or bimonthly encounter calls but we will continue to schedule study follow up visits.

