**C.3.d. Exclusion Criteria Determined During Initial Screening Phone Call with Potential Subjects.**

- Refusal or inability to consent to an in-person baseline visit.
- Planning to leave the area prior to the anticipated end of participation.
- Inability or unwillingness to come to the Durham VAMC for baseline-, 6-, 12-, and 18-month study visits.
- Does not have reasonable access to a telephone.
- Does not speak English.
- Resident in nursing home or receiving home healthcare.
- Severely impaired hearing or speech (Patients must be able to respond to phone calls.)
- Severely impaired vision (Patients must be able to read mailed material).
- At the time of potential enrollment, participating in another ongoing hypertension, diabetes, cholesterol, or cardiovascular disease clinical trial.
- Patient reports currently receiving dialysis (may or may not be at the VA).
- Type 1 diabetes, as reported by the patient.
- Patient indicates she is pregnant or planning to become pregnant in the next two years.
- Patients with class IV CHF, dialysis-requiring renal disease, and type 1 diabetes have blood pressure and/or blood sugar management that are beyond the scope of a primary care pharmacist. Exclusion of patients with COPD requiring oxygen and class IV CHF is done (similar to our exclusion of patients with metastatic cancer) to keep patients with end-stage or near end-stage illness out of the study, both because their life expectancies minimize the importance of hypertension control.

[figure not shown]

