### **C.20.d. Adherence to Blood Pressure Medication.**

We will assess adherence using **prescription refill data**. These data will be extracted from the Durham VistA (electronic health record) system or national VA pharmacy databases that contain pharmacy information

from the VA electronic health record. Commonly used in pharmacoepidemiology, refill data are used to estimate the supply of medications patients have and are often expressed as a Medication Possession Ratio (MPR). In this study, we will use ReComp, which was developed and validated using pharmacy refill data. ReComp is more flexible than previous measures in handling longer prescription periods for chronic cardiovascular medications. ReComp also accounts for multiple dimensions of adherence behavior (e.g., late fills, use of overstocked medication) and is more precise than previous refill approaches when used in repeated measures over short time periods. We will utilize ReComp to measure adherence with antihypertensive medication [considered together for adherence]. An aggregate ReComp-based MRP measure will be calculated for each patient by averaging ReComp MPR for individual drug classes covering six month time intervals beginning 1 year prior to patient randomization and continuing during the 18 months of the intervention or booster control. Other methods for calculating medication adherence using prescription refill data may also be examined using the same data.

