#### **D.8. Intention-to-Treat Analysis**

All of the proposed primary and secondary analyses focus on the effect of the intervention group as compared to the control group. We, therefore, plan to use the Intention-to-treat assumption for all analyses. In this assumption, patients are analyzed as part of the group to which they are randomized, regardless of treatment compliance.

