### **J.1.d. Supplemental Data Extraction.**

In order to complete health economic, medication adherence, and exploratory analyses, we will extract data from the VA electronic health record or related linked administrative data on healthcare events for the full sample from the study. With appropriate informed consent and HIPAA authorization, clinical and utilization data from VA electronic health record or related linked administrative data may be obtained for the period prior to study enrollment.

The extracted data will be stored on a VA HSR&D server that is compliant with regulations described in VA Directive 6500 and located on the VA FISMA certified network. The servers are located within the VA protected environment (i.e. behind the VA fire wall) and are physically located within the secured server room at the offices of the Durham VAMC HSR&D Center of Excellence. Physical access to the servers is limited to authorized VA OI&T personnel in accordance with VA directive 6500. Only HSR&D study staff at the Durham VAMC will have access to data stored on the server. All staff has and maintain VA required training, maintain study data exclusively on HSR&D servers, follow accepted security practices such as locking computer with CTRL-ALT-DEL when not at the computer, and adhere to other regulations laid out in VA Directive 6500. Destruction of data will be done in accordance with all VA and VHA records disposition requirements.

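### D.5 ties refill adherence to local VA pharmacy records although C.20.d also allows a national source and movers within the VA stay in the trial; if the local source is used, their later fills are missed and H4 takes in falsely low values

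*Protocol*

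**What the plan says.** The analysis section for H4, D.5, states, with a reference to C.20.d: "medication adherence will be calculated by applying the ReComp algorithm to local VA pharmacy records". It calculates adherence at baseline and for each follow-up month, and tests the difference between arms at 18 months.

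The section it cites, C.20.d, is wider. The refill data may be "extracted from the Durham VistA (electronic health record) system or national VA pharmacy databases". Section J.1.d, on extraction for the economic, adherence and exploratory analyses, is also worded as alternatives: "we will extract data from the VA electronic health record or related linked administrative data on healthcare events for the full sample from the study".

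For a patient who switches to another VA facility, C.3.b says "we will no longer conduct monthly or bimonthly encounter calls but we will continue to schedule study follow up visits". Under D.8, "patients are analyzed as part of the group to which they are randomized, regardless of treatment compliance". Sections C.19 and I.3 have separate instructions for participants whose care has moved to a different VA facility, so the protocol expects some.

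**The concern.** A refill measure knows only the fills in its source. For a patient who stays at Durham, the local and national sources should agree. For a patient who moves within the VA, the local source stops recording at the move while the patient may go on filling every prescription elsewhere. D.5 describes the ratio as the share of days on which drug was available, so absent fills read as absent drug.

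That makes this different from an ordinary missing outcome. Section D.7 deals with values that are missing through drop-out, missed assessments or item non-response, and relies on likelihood methods under missing at random. A low ratio computed from an incomplete source is an observed number, and those methods take it at face value.

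At stake is a named secondary hypothesis (A.1.d). Its month-18 contrast would carry added noise, some shrinkage toward zero and, if moves were unequal between arms, bias. In the dichotomous version of the outcome, a mover whose recorded supply had run out would be classed as nonadherent whatever was filled elsewhere.

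**Working it through.** The protocol states no figure for this point that could be reproduced. The check is first a comparison of sections, then a bound.

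**Sections side by side**

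- D.5 names the local source only.
- C.20.d names Durham or national, without saying which applies to whom.
- J.1.d leaves the source open.
- C.3.b and D.8 keep movers in follow-up and analysis.
- No section says how refill data are obtained for a patient after a move.

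**Bound on the effect if the local source is used**

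Assumptions, none of them from the protocol: true ratio with mean 0.85 and SD 0.20 (variance 0.04); a share p of patients in each arm have moved; every mover's measured ratio is 0 by month 18.

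- Drop in arm mean = p × 0.85.
- Variance = (1 − p) × 0.04 + p(1 − p) × 0.85², with 0.85² = 0.7225.
- Variance multiplier = variance / 0.04.

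| p | Drop in mean | Variance | SD | Multiplier |
|---|---|---|---|---|
| 2% | 0.017 | 0.0392 + 0.0142 = 0.0534 | 0.23 | 1.33 |
| 5% | 0.043 | 0.0380 + 0.0343 = 0.0723 | 0.27 | 1.81 |
| 10% | 0.085 | 0.0360 + 0.0650 = 0.1010 | 0.32 | 2.53 |

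At 5%, precision matches that of 0.04 / 0.0723 = 0.55 of the sample. These are marginal variances at one time point; the repeated-measures model is not represented.

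**Effect on the contrast**

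- Equal move rates: each arm mean is multiplied by (1 − p), so the drop largely cancels and a true difference shrinks by the factor (1 − p). At p = 5% it keeps 95% of its size.
- Unequal move rates: bias is about 0.85 × the difference in rates. A 3-point difference gives 0.03 × 0.85 = 0.0255, about 0.026.

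**Why these are upper bounds**

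C.20.d says ReComp accounts for late fills and overstocked medication, so recorded stock carries forward and the fall is gradual. A patient who moves shortly before month 18 may show little effect. The relevant p is the share of patients whose recorded stock has run out by then, which cannot exceed the share who have moved.

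**The case against.** A reader might infer that every mover will be scored as taking no medication from the move onward. The protocol does not support that, for four reasons.

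- The D.5 sentence opens by deferring to C.20.d, where national databases are already an option. The protocol does not commit to a local-only source.
- No section writes a rule that scores a period without a local fill as 0.
- ReComp's carry-over delays any fall. Over the six-month intervals of C.20.d, a move within an interval would give a partial value.
- The group is probably small. C.3.d excludes anyone "Planning to leave the area prior to the anticipated end of participation", and C.3.b requires that most care be received at Durham or an affiliated clinic.

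All four stand against the stronger reading. They do not remove the narrower one. The deference to C.20.d settles nothing, because C.20.d leaves the source open and the one section that specifies the calculation narrows it to local records. The two sections also differ on the interval, six months in C.20.d against one month in D.5, so the cross-reference cannot be relied on to override D.5. Carry-over postpones the fall but recorded stock is finite. The screening exclusion removes only those who already plan to leave.

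A reader might also infer a bias between arms, or a distortion of the planned look at over-supply and systolic pressure. Nothing suggests that moves differ by arm. Falsely low ratios would not place movers in the over-supply range above 1.

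**Conclusion.** The point holds in conditional form. D.5 and C.20.d do not agree on the source, and following D.5 as worded would miss the later fills of patients whom the protocol keeps in the trial. Their adherence would be understated as observed data that D.7 does not correct. If the national source is used, the problem disappears for moves within the VA.

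The mismatch between the sections is certain; the size is not. The mean loss of 0.017 to 0.085 and the variance multiplier of about 1.3 to 2.5 rest on an assumed mover rate of 2% to 10%, an assumed mean and SD, and every mover reaching 0 by month 18. The likelier harm is lost precision with slight attenuation. The primary outcome is not affected. It is worth correcting because the correction is cheap and the national source captures more than the local one.

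**What to change.** In D.5, replace the reference to local records with the national VA pharmacy database already named in C.20.d, for all patients in both arms and for every period, including the pre-randomization baseline. In C.20.d, remove the either/or so that both sections name the same source. Applying one source to everyone avoids having adherence measured differently for movers and non-movers.

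The cost is wording and one extract. National pharmacy extracts are already planned for the cost analysis in C.20.c, and no visit, assessment or patient contact changes.

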### **C. 13. Intervention Component – Pharmacist-Directed Algorithmic Medication Management [high/level 2 resource intensity]**

Many patients require medication intensification to achieve targets for BP. Appropriate medication management requires accurate and timely information on the patient's current level of disease control, treatment adherence, evidence-based recommendations, and potential barriers to successful implementation. Patients who meet criteria for high/level 2 resource intensity disease management will receive medication management from a clinical pharmacist, who will be backed up by an MD ([name] or his appropriately licensed back-up/replacement who could be a mid-level provider). Pharmacists are authorized to make medication changes according to accepted treatment algorithms and based on their scope of practice. Via CPRS, the pharmacist will also communicate these changes to the patient's PCP. While pharmacists may collaborate with the patients' providers when clinically indicated, they do not have to rely on providers to make the changes. The goal of the medication component of the intervention is not to replace clinic based management, but rather to supplement it based on home BP readings in order to more efficiently implement interventions that may otherwise be left until the next provider appointment. The pharmacist will attempt to contact patients every month while they are in the high-intensity titration level of the intervention. At the pharmacist's discretion, patients may be asked to come to the Durham VAMC for an in-person meeting, however, most interactions will be conducted over the phone. During each encounter, the pharmacist will have information from both CPRS and the behavioral-telephone calls conducted as part of the intervention so information on such topics as patient medication and barriers to adherence can be available. During the initial encounter the pharmacist will assess the patient's medication adherence, review all BP related medications, discuss the purpose of each medication, and the appropriate administration of each medication. While not explicitly planned, the pharmacist (or appropriately licensed clinical backup) may discuss other medicines if he or she feels that this is needed to appropriately manage BP medication. At subsequent contacts the pharmacist will review any medication changes with the patients and update patients' medication lists. All calls will be indicated with a note in the Durham VAMC electronic health record.

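### The continuous H4 test counts oversupply as better adherence, and only the intervention arm has study-driven medication changes that can create it

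*Protocol*

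**What the plan says.** H4 (A.1.d) claims a greater improvement in medication adherence in the titrated arm.

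- **Inputs.** D.5 applies ReComp to three pharmacy fields: "medication name, date dispensed, the number of days supply dispensed".
- **Scale.** D.5 states that "ReComp values can be any value greater than or equal to 0". Only 0 to 1 is given an adherence meaning; above that, D.5 speaks of "values over 1 representing oversupply of medication". No cap is stated.
- **Test.** "The impact of the intervention upon continuous medication adherence will be tested with a general linear model", using PROC MIXED to "test the difference in medication adherence at 18 months". D.5 adds: "We will operationalize adherence as both a continuous and dichotomous variable as described above under measures". The dichotomous form goes into a generalized linear mixed model.
- **Aggregation and interval.** C.20.d builds one value per patient by "averaging ReComp MPR for individual drug classes covering six month time intervals". D.5 makes the person-month the unit of analysis.
- **Study-driven changes.** C.13, for High/Level 2 patients: "Pharmacists are authorized to make medication changes according to accepted treatment algorithms and based on their scope of practice". Table 2 expects about 70 of 200 intervention patients at that level at baseline. Under C.16, control patients receive LPN calls and no study pharmacist.

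**The concern.** A continuous outcome with no ceiling, compared by means, treats every extra unit as more of what is being measured. D.5's own definition breaks that reading at 1. Up to 1, a higher value means more days covered; beyond 1, it means more tablets in the cupboard. A patient at 1.3 counts in the H4 contrast as 0.3 better than a patient who was fully supplied.

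If surplus arose equally in both arms this would mostly add noise. Here there is a route by which it need not. When a drug or strength is changed before the previous fill is used up, old and new supply overlap on paper. The intervention includes a clinician whose task is to make such changes, and the control arm does not. Primary care providers can change prescriptions in both arms, so only the excess in the intervention arm matters. That excess is part of the treatment being tested. At stake is whether a positive continuous H4 result reflects patient behaviour or partly the mechanics of dispensing.

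**Working it through.** The protocol gives no power, SD or effect size for H4, so there is no figure to reproduce. The check asks how large the upward shift could be.

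**Inputs from the protocol:** 70/200 = 35% of the intervention arm at High/Level 2 at baseline (Table 2); 200 randomized per arm and 15% attrition (D.3), so 170 to 200 per arm; a six-month interval and averaging over classes (C.20.d).

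**Assumptions:** full adherence in both arms; a 180-day interval; 90-day fills; one within-class change at day 30; two classes per patient; 10% to 35% of the arm at High/Level 2 in the interval; half or all of these having such a change beyond what occurs in the control arm; SD 0.15 to 0.30. The calculation uses a plain ratio of days supplied to days in the interval, as a stand-in for ReComp.

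**Per patient.** The old fill supplies 90 days and the new drug covers days 30 to 180, which is 150 days.
- Changed class: (90 + 150)/180 = 1.333.
- Two-class average: (1.333 + 1.000)/2 = 1.167.
- With each class capped at 1: 1.000.

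**Shift in arm mean** = share at High/Level 2 × share changed × (1.167 − 1).
- 0.10 × 0.5 × 0.167 = +0.008
- 0.35 × 0.5 × 0.167 = +0.029
- 0.35 × 1.0 × 0.167 = +0.058

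**Sensitivity of the last figure.** A change at day 60 gives +0.029. Three classes give +0.039. One class gives +0.117, an extreme in which every High/Level 2 patient takes a single class and has it changed.

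**Yardstick.** Minimum detectable difference at 80% power, two-sided 5% = (1.960 + 0.842) × SD × √(2/n):

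| SD | n = 170 | n = 200 |
|---|---|---|
| 0.15 | 0.046 | 0.042 |
| 0.20 | 0.061 | 0.056 |
| 0.25 | 0.076 | 0.070 |
| 0.30 | 0.091 | 0.084 |

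At SD 0.20 and n = 170 the two-class shift runs from 0.008/0.061 = 0.13 to 0.058/0.061 = 0.95 of a detectable difference.

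**Where the cap acts.** It must be applied to each class before averaging. Class values of 1.333 and 0.667 average to 1.000 uncapped, so surplus in one class hides a shortfall in the other. Capped first, they give (1.000 + 0.667)/2 = 0.833.

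**Interval.** In the same example with 30-day months, crediting supply to the days it would cover, the changed class scores 1, 2, 2, 1, 1, 1. The mean is again 8/6 = 1.333, but the surplus sits in two months at 2.0. With person-months, an 18-month contrast would pick up larger values in fewer patients. The size therefore cannot be fixed until C.20.d and D.5 agree.

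**The case against.** **ReComp is a cited, validated algorithm, and C.20.d says it accounts for overstock.** Its overlap and denominator rules lie in sources not at hand, and the figures above are for a plain supply ratio, so they illustrate and do not estimate. That stands. It does not remove the point, because D.5 says of the value it will analyse that it can exceed 1 and that the excess is oversupply.

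**Leaving values above 1 in is deliberate.** D.5 wants to study oversupply and its association with SBP. That is a fair aim, but it calls for a separate analysis and does not justify scoring surplus as adherence in the H4 test.

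**A dichotomous analysis is also planned, and self-reported adherence is collected at every study visit in both arms.** In a dichotomous analysis, supply beyond the cut-off adds nothing, so the artefact is limited there. It is not wholly removed, since surplus in one class can lift the average of a patient short in another, and C.20.d, to which D.5 points, states no cut-off for the refill measure. Self-report is listed in C.21 among mechanism measures and covariates and is not the H4 outcome.

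**The larger inputs are demanding.** They require every High/Level 2 patient to have an overlapping change in the interval bearing on month 18, while controlled patients move to booster at 6 or 12 months. This is fair, though C.9.b and C.9.c also allow patients to be moved up later.

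**A stronger reading is tempting:** that a class the pharmacist stops is scored as non-adherence, so that H4 is distorted in both directions. No stop date is among the three listed inputs, but the documents do not give ReComp's denominator rule and so do not show this. The missing cap bears only on the upward direction.

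**Conclusion.** The point holds for the continuous H4 test. By D.5's own definition, values above 1 do not measure days covered, yet they raise the mean that is compared. Study-driven changes that can produce them occur in the intervention arm only. The size is unknown: under the stated assumptions it is about +0.01 to +0.06, from negligible to about the size of a detectable difference at SD 0.20. The change rates, the SD, the number of classes and the supply-ratio stand-in for ReComp are all assumptions.

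A reader might infer that H4 cannot be read as adherence at all, or might attach a false-positive rate to it. Neither is supported. The first overlooks the dichotomous analysis and the lower end of the range; the second needs change rates, an SD and ReComp rules that the protocol does not give. This is a correction worth making before analysis and does not invalidate the hypothesis.

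**What to change.** 1. In C.20.d and D.5, cap each drug-class value at 1.0 before averaging, for the continuous H4 test.
2. Report oversupply, and its association with SBP, as a separate analysis by arm.
3. Keep the uncapped value as a sensitivity analysis.
4. State one measurement interval in both sections, six months or the person-month.
5. As a supporting step, confirm how ReComp treats prescriber-ordered stops and switches. If it does not close a class at the stop, end that class's denominator at the recorded order stop date, from the health record, in both arms. The log of pharmacist changes (C.15) would not serve alone, because it covers only the study pharmacist's changes.

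The cost is protocol or SAP wording and modest programming; item 5 may add extraction of order dates. No new patient data collection is needed. The downside is that the H4 value itself no longer shows oversupply, which is why items 2 and 3 retain it.
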